# 7.3 Sample stratification

Sample could be stratified based on factors such as patients' characteristics (gender, age), Knee OA radiological characteristics, use of conventional medication (NSAIDS, corticosteroid injections), history of interventional treatment in the affected knee (open surgery, arthroscopy, arthrocentesis) and impairment associated with the perceived pain caused by the OA. These variables will be analyzed through statistic tests for independent measures.

### 8 ETHICAL CONSIDERATIONS

#### 8.1 General Considerations

The present protocol will be conducted in full concordance with principles of the "Declaration of Helsinki" (Helsinki, 1964) amended by the 64th World Medical Assembly (Fortaleza, 2013), the Good Clinical Practice.

The ESTIK survey correspond to Post-Market Clinical Follow-up (PMCF) studies conducted using CE marked devices according to the Council Directive 93/42/EEC concerning Medical Devices (June 14th, 1993, last amended by Directive 2007/47/EC of the European Parliament and of the Council of on September 5th, 2007) which represents that Suplasyn® should be recommended following the Good Clinical Practice principles, thus to be use in the usual manner in accordance with the instructions for use (leaflet) supplied with the marketed products.

### 8.2 Evaluation of benefit-risk for patients during study

The participation in this study does not involve or represent an increased risk for patients and does not modify the usual therapeutic practices. Participants will be not subjected to additional or extraordinary diagnostic tests other than those normally indicated for these patients.

# 8.3 Safety Assessment

Adverse events observed by the doctors or reported by the patients spontaneously or following a non-leading questions, will be collected on patient data form. Particular attention will be paid to local painful reactions at the injection site, post-injection reactions (i.e. effusion, skin rush, swelling, warmth) and acute pseudoseptic arthritis. (36)

#### 8.4 Patients Information Sheet and Consent Form

All patients will receive an information sheet with a description of the study and its procedures as well as a consent form to be signed. It is important to remark that all patients whose data will be recorded should be informed of the nature of the study and have to give their informed consent (or oral consent with signature of a witness, i.e. nurse or relative) for the collection of their data, since this project is an observational study thus the decision to include a patients in it must be considered after the recommendation of Suplasyn®.

#### 8.5 Ethical Committee Evaluation

All study materials, including protocols and surveys, have been developed by [name], and have been approved by the Ethics Committee for Clinical Research of the Krnov Hospital (Czech Republic).

#### 8.6 Data Protection

Researchers will guarantee the anonymity of each patients participating in the study and will protect his/her identity from third-parties or non-authorized figures.

No personal information which may allow identifying patients will be recorded. Patients' identity will be codified in the CRFs and only each researcher will have access to this data in cases of verification or clarifications.

All the data recorded in the surveys will be hosted in secured servers with restricted access, which are also subjected to Spanish Data Protection laws (database files are notified and registered at the Spanish Data Protection Agency) according the "Ley Orgánica 15/1999, 13 de diciembre de 1999".

### 8.7 Interference with researcher prescription habits

Suplasyn® should be recommended following the Good Clinical Practice principles, thus to be use in the usual manner in accordance with the instructions for use (leaflet) supplied with the marketed products.

The assignment of the patient to a particular therapeutic strategy is not decided in advance by a trial protocol but falls within current practice and the use of the medical device is clearly separated from the decision to include the patient in the study.

No additional diagnostic or monitoring procedures shall be applied to the patients and epidemiological methods shall be used for the analysis of collected data.

# 9 PRACTICAL CONSIDERATIONS

# 9.1 Work plan

All researches will have to register to be assigned with a personal id and password for access to study online surveys. Once the researcher has signed the *researcher commitment form* and have received a confirmation of his/her registration can proceed to the inclusion of data.

Patients will be selected from those who accomplish inclusion criteria, based on the consecutive sampling technique. Researcher will proceed to explain patient about the study and ask for a signature on the *consent form* prior to the inclusion.

It is important to keep in mind that the recommendation with Suplasyn® for the viscosupplementation of the affected knee is not conditioned to the development of the study or the inclusion of a specific patient in this study.

Data will be recorded by the researcher in an online electronic Case Report Form (eCRF) to which will access with their id and password. The online platform will assign to each patient an automatic and unique code which will allow registering his/her clinical information throughout all study visits for the later generation of a database and an analysis of the final results. The eCRF does not contain any patients' personal information and the researcher is committed to keep the access information and the content of the eCRFs in complete anonymity, besides the obligation to accomplish with the principles and laws applicable in his/her local context, being fully responsible for the truthful of the provided data.

- On visit 1 (baseline) patient will receive the first intraarticular injection of 2ml of Hyaluronic
  Acid Suplasyn® in the affected knee following the product instructions leaflet and according to
  standard measures for these types of procedures. In this visit, patient will also have to complete
  the Patient eCRF which includes the OKS.
- On visit 2 (administration of the second HA injection, one week after first injection) and Visit 3 (administration of the third HA injection, one week after second injection) adverse events should be investigated. In case the researcher obtains as a response to the question

"How did you feel since your last visit" any adverse event since prior visit, the *Adverse Event* Form should be completed and sent to the study coordinator.

- Visit 4 (1 month after injection): Researcher will complete the eCRF corresponding to that
  visit by recording data on patient's consumption of any pharmacological treatment for pain
  during the previous month, recording data on frequency, dose and type of drug used. In this
  visit patient will have to assess his/her perceived pain with the VAS, grading the intensity of this
  symptom "during daily activities" and "at rest/at night".
- Visit 5 (6 months after injection): The procedure will be the same that on visit 4.

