# 3.2 Secondary Objectives

- To evaluate the safety profile and adverse events (AEs) of Suplasyn® 2ml injections.
- To evaluate the concomitant consumption of permitted rescue medications (analgesics, NSAIDS) throughout the study.
- To evaluate characteristics of the beneficiary population (Intended to treat).

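### Section 9.1 schedules the adverse-event question only at Visits 2 and 3, so no scheduled enquiry covers the third injection or weeks 2 to 26

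*Protocol*

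**What the plan says.** The first secondary objective in section 3.2 is "To evaluate the safety profile and adverse events (AEs) of Suplasyn® 2ml injections". The Study Rationale in section 2 describes a 26-week study of effectiveness and safety, and section 6.1 lists safety among the main variables.

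Section 9.1 is the only place that gives the AE enquiry a time and a wording. It does so at Visit 2, when the second injection is given, and at "Visit 3 (administration of the third HA injection, one week after second injection) adverse events should be investigated". The investigator asks an open question about the interval, and the Adverse Event Form is completed if the answer reveals "any adverse event since prior visit".

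For Visit 4, at one month, the investigator completes the eCRF for that "visit by recording data on patient's consumption of any pharmacological treatment for pain", and the patient rates pain on the VAS. For the six-month visit the entry reads "Visit 5 (6 months after injection): The procedure will be the same that on visit 4". Neither entry mentions AEs.

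Sections 6.2 and 8.3 carry a general rule: AEs may be seen by the doctor, volunteered by the patient, or elicited by a non-leading question, and they go on the patient data form. Section 8.3 adds: "Particular attention will be paid to local painful reactions at the injection site, post-injection reactions". Neither section names a visit.

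**The concern.** The product is given three times, and the protocol directs special attention to what happens after an injection. The enquiry at Visit 3 is made when the third dose is given, so it can only ask about the second. Followed as written, the work plan seeks events in one way after injections 1 and 2 and in an unspecified way after injection 3 and for the rest of follow-up.

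Two results are at stake. The first is the share of patients with any reaction, which may be understated if events after the third injection are sought less thoroughly. The second is the time course. Section 7.2 plans repeated-measures tests for the secondary as well as the primary objectives, to describe change over the visits. If the method of seeking events changes after week 2, a fall in reported events could reflect the method alone. No analysis can recover events that were never asked about, so this belongs to data collection and not to detail that a statistical analysis plan would supply.

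**Working it through.** The protocol gives no AE rate, capture rate or precision target for safety, so there is no figure of its own to reproduce.

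**Step 1: match injections to enquiries.** Injection times are from section 5.5, visits from section 9.1.

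| Injection | Given at | Scheduled enquiry looking back on it |
|---|---|---|
| 1 | Visit 1, Day 1 | Visit 2 |
| 2 | Visit 2, Week 1 | Visit 3 |
| 3 | Visit 3, Week 2 | none listed |

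One of three injections is not covered. For the 300 patients of section 5.6 that is 300 of 300 × 3 = 900 planned injections.

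**Step 2: match follow-up time.** Section 5.4 sets 26 weeks from the first injection. The last scheduled enquiry is at week 2, which leaves 26 − 2 = 24 weeks, and 24/26 = 92%. This is a share of calendar time, not of expected events.

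**Step 3: check whether another section repairs the gap.** Section 9.1 also omits the OKS at Visits 4 and 5 and the VAS at Visit 1. Section 6.2 repairs both by fixing each instrument at baseline, 1 month and 6 months. For AEs, sections 6.2 and 8.3 name sources and a form but no time. The gap stays open.

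**Step 4: illustrate the possible size.** The inputs are assumptions: reaction risk p per injection, independent between injections; full capture after injections 1 and 2; a fraction s of third-injection reactions captured.

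- True share of patients with at least one reaction: 1 − (1 − p)³
- Observed share: 1 − (1 − p)²(1 − ps)

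At p = 5% the true share is 1 − 0.95³ = 14.3%. With s = 0.5 the observed share is 1 − 0.95² × 0.975 = 12.0%. With s = 0 it is 1 − 0.95² = 9.8%. Each cell below shows the observed share, with the relative shortfall in brackets.

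| s | p = 2% | p = 5% | p = 10% |
|---|---|---|---|
| 1 | 5.9% (0) | 14.3% (0) | 27.1% (0) |
| 0.75 | 5.4% (8%) | 13.1% (8%) | 25.1% (7%) |
| 0.5 | 4.9% (16%) | 12.0% (16%) | 23.1% (15%) |
| 0.25 | 4.4% (24%) | 10.9% (24%) | 21.0% (22%) |
| 0 | 4.0% (33%) | 9.8% (32%) | 19.0% (30%) |

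The relative shortfall hardly depends on p. It depends on s, and the protocol fixes nothing that would locate s.

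**The case against.** The best defence is that section 9.1 is a practical summary and that its silence does not cancel the general rule in sections 6.2 and 8.3. That rule offers three routes, one of them solicited, and sets no visit limit. Patients are seen at 1 and 6 months, when it can be applied. The list in section 9.1 is demonstrably incomplete: read literally, it would mean that the OKS is never measured after baseline. The eCRF and the Adverse Event Form are not part of the protocol text, so the Visit 4 and 5 pages may already carry an AE field. Safety is also a secondary objective in a single-arm descriptive survey with no precision target.

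Much of this stands. A reader might infer that everything after week 2 rests on spontaneous report. Sections 6.2 and 8.3 contradict that, since they also admit doctor-observed events and non-leading questions. A reader might also infer that the gap conceals any rise in reactions with repeated exposure. That goes too far, because injections 1 and 2 can still be compared.

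The appeal to incompleteness does not stand in full. The OKS and VAS omissions are repaired by explicit times elsewhere; the AE omission is not. A general permission to ask leaves each site to decide whether to ask, and when.

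**Conclusion.** The point holds as a gap in scheduled ascertainment. The only timed AE enquiry ends at Visit 3, before the third injection can be assessed and with 24 of 26 weeks still to run. No other section sets a later time. Ascertainment after the third injection may therefore be incomplete and may differ between sites.

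It is tempting to go further and say that the reported rate is biased low by about a third. The document does not support that. The 32% figure is the extreme case in which no third-injection reaction is captured, which sections 6.2 and 8.3 make unlikely; with full capture the shortfall is zero. At an assumed 5% risk the range is 0 to 32%, and it rests on independence between injections and full capture after the first two. Under-ascertainment is a risk here, neither shown to occur nor measurable from the protocol.

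Severity is moderate: the first-listed secondary objective is affected, and the primary endpoints are not.

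**What to change.** Reconcile section 9.1 with sections 6.2 and 8.3:

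- State the same non-leading AE question and the Adverse Event Form at Visits 4 and 5, for the period since the preceding visit.
- Record the onset date, so that each event can be placed after injection 1, 2 or 3 or later in follow-up.
- Report AEs by interval: after injection 1, after injection 2, after injection 3, and to week 26.

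The cost is one question at two visits that already take place, with no extra visit or diagnostic procedure, so section 8.7 is respected. The change is needed before data collection, since later repair would depend on memory.

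A limitation remains. Taking the 4- and 26-week assessment times of section 7.2 as counted from the first injection, the look-back would be about 4 − 2 = 2 weeks at Visit 4 and 26 − 4 = 22 weeks at Visit 5, against one week at Visits 2 and 3. Recall will be weaker at the later visits, and the report should say so when it compares intervals.

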#### 9.2 Interim and Final Reports

A final report will be developed based on the final results.

#### 9.3 Dissemination of results

All data collected during this study will be used globally and not individually. Researchers who participated in the project will receive a copy of the final study report with the results obtained and this document shall be confidential.

Scientific publications and/or materials including conference presentations will be considered, always making explicit reference to the study.

